5.10 Compensation

Participants can be compensated up to a total of \$430 for full participation in this research study. Participants will receive \$10 for the screening blood draw and \$40 for completion of the baseline survey. For completion of the follow up surveys at 1, 3, 6, and 12 month study timepoints participants will receive \$20 per survey. In addition to survey completion, participants who report quitting smoking on the 6 and 12 month surveys will be asked to provide either a saliva sample or complete a CO test, used for biochemical validation of self-reported abstinence. For completion of biochemical validation at the 6 and 12 month timepoints, participants will receive \$100 per timepoint. \$50 will be offered for travel reimbursement at each of the 6 and 12 month timepoints. Similar compensation has been used in a previous research studies and was deemed by the VUMC Institutional Review Board (IRB) to be an appropriate, non-coercive, amount of funds for involvement in a clinical research project.

5.11 Retention

Baseline visit: Retention efforts begin at baseline by ensuring that everything possible is done to maximize the likelihood of the participant enjoying the experience of participating in the study. Retention is supported by explaining the informed consent and what may happen in the study, and by collecting complete contact information, including both the address where the participant currently resides as well as multiple contact numbers if available. Participants will be asked to provide contact information for at least one alternative contact who may know their whereabouts if we are ever unable to get in touch with the participant. Alternative contacts can include friends or family members; an alternative contact who is a close relative (ie. spouse, significant other, or caregiver) can opt to be the participant's proxy. Participants will also be asked to provide an email address. The Interactive Voice Response (IVR) that all participants receive beginning 3 days after study enrollment and spanning 3 months also promotes retention through repeated contact via phone, text, or email according to the participant's preferred method of contact.

Additional strategies to promote retention and follow-up: Study participants will be asked to contact the study team if their phone number, address or PCP information changes between study visits; if needed, study staff may assist in re-establishing a primary care provider. The study team may collaborate with the participants PCP by contacting the PCP's clinic staff and/or sending an electronic message through the EHR to the PCP directly to inquire about the status of a patient for follow up on medication adherence, smoking status, or general issues regarding follow up participant contact information. For assessing abstinence, if the participant cannot complete the salivary cotinine test or remote CO monitoring and instead must come into the clinic for the CO breath test, we will make all efforts to coordinate with the patient during any pending appointments at VUMC so that they can take the CO test on a day when they are already scheduled to be at VUMC (e.g., study RA will travel to the One Hundred Oaks clinic or other VUMC clinics to meet participant).

6.0 Risks

The potential risks to subjects are not more than those of standard smoking cessation treatment. These include possible psychological distress from speaking with a counselor or answering questions about their smoking, discomfort or bruising from a blood draw, loss of confidentiality due to breach of protected health information, potential side effects of the process of quitting smoking, and potential side effects of smoking cessation medications, all of which are FDA-approved.

6.1 Smoking Cessation Medication Side Effects

In order to protect against potential risks associated with smoking cessation pharmacotherapy, this study involves FDA-approved medications according to label usage for smoking cessation aids. There is a risk of adverse side effects from FDAapproved smoking cessation medications, but this risk is not higher than that experienced by people taking the same medications outside of this research study.

The smoking cessation treatments in this study consist of counseling from trained tobacco treatment counselors in combination with safe and effective FDA-approved medications prescribed by the participants' inpatient team and/or PCPs. This combination of medication and counseling is the standard of care for smoking cessation treatment, and for those who successfully quit smoking, results in prolongation of life and improved quality of life.

Medication eligibility will be reviewed by two separate members of the study team (e.g., CTTS and PI or study coordinator and PI) to identify potential contraindications to nicotine replacement or varenicline.

- Nicotine replacement therapy (NRT): NRT is generally very safe, and several preparations have been sold over the counter for decades which is an indication of the FDA's view of their relative safety. The most common side effect of the patch is skin irritation or itching where the patch is applied, which is commonly managed by rotating patch sites and/or applying an OTC corticosteroid cream (such as 1% hydrocortisone). For nicotine lozenge/gum the most common side effects are mouth irritation, heartburn, hiccups. Many of the side effects of the lozenge/gum can be avoided by proper technique of the medication. For the nicotine inhaler and nasal spray, the most common side effects can include mouth/throat irritation, coughing, runny nose, watery eyes. In rare cases dizziness, headache, nausea, and rapid heartbeat can occur.
- Varenicline: Common side effects of varenicline include nausea and other gastrointestinal symptoms, sleep disturbance, and vivid dreams. The FDA-mandated EAGLES trial has established these medications as safe and effective. [52]
- Written and verbal instructions will be provided to patients to contact their PCP or the research study staff in case of adverse events that could possibly be medication-related. The IVR system (automated calls from approximately 3-days post hospital discharge (hospitalized patients) or 3-days post randomization (outside of hospital) to approximately 12 weeks post discharge or randomization, respectively) which helps protect participants by providing them with "on-demand' counseling designed to trouble-shoot any difficulties with study medication.

Advice for Participants

Participants may want to discontinue their medications due to possible side effects. Before medication is discontinued participants will be encouraged to adjust their medication routine. For example, placing the patch on a different arm or place on the body and possibly even recommending a different brand of patch if allergic to latex or having a reaction to the adhesive. For oral NRT, patients will be reminded of proper usage of the product (gum, lozenge, inhaler, etc.) in order to avoid some of the most common and undesirable side effects.

For certain common side effects of FDA approved smoking cessation medication, such as mild-moderate gastrointestinal (GI) problems or mild-moderate sleep problems, study staff will provide the following advice:

- For moderate GI problems, study staff will remind the participant of proper administration (e.g., taking varenicline medication with food and water or milk) and reiterate that these side effects typically improve within 2-3 weeks after initiation of medication.
- For moderate sleep problems, study staff will remind participants of proper use (e.g., may remove patch at night or take the evening dose of varenicline earlier in the day or skip the evening dose, etc.) and will reiterate that the side effect typically improves within 2-3 weeks after initiation of medication
- Participants will also be reminded that many of these symptoms can accompany the process of quitting smoking *itself*, regardless of medication use.

For participants who normally drink caffeine or take caffeine pills, study staff will make the participant aware that chemicals (i.e., polyaromatic hydrocarbons) in cigarette smoke metabolize/break-down caffeine, so generally smokers "need" more caffeine when they are smoking at their usual rate. However, as smoking is reduced or stopped altogether, caffeine levels may rise, causing a person to feel jittery, irritable, nauseated, etc. Participants may be instructed to reduce caffeine intake by half, and thereafter to adjust caffeine intake to comfort.

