Informed by our preliminary data, we propose a scientifically rigorous RCT design of approximately 1,000 adult CMS beneficiaries or those with prescription coverage, who are daily smokers hospitalized at Vanderbilt University Medical Center (VUMC) to compare effects of MIST vs. UC on: abstinence (1° aim), implementation in clinical practice (2° aim), and health care utilization and mortality (exploratory). All participants will receive UC for tobacco treatment, including: (1) bedside tobacco consult; (2) a prescription for varenicline or NRT; and (3) automated phone calls via TelASK to promote engagement after study enrollment. Medication prescriptions will be NMR-guided for MIST participants and patient-provider selected for UC participants. Type of NRT (e.g., inhaler, gum, patch, etc.) will be informed by insurance type. For example, some plans in Medicare Part D cover only prescription NRT (inhaler, nasal spray) while most state Medicaid programs only cover over-thecounter (OTC) meds (e.g., patch, gum, lozenge). The research team will work with PCPs and their staff to facilitate smoking treatment after study enrollment and will track pharmacy records for PCP-generated prescriptions for patients who continue smoking. PCPs of patients in MIST will be given the NMR results, while PCPs of UC participants will not. Phone surveys will be conducted at approximately 1, 3, 6, and 12 months to assess medication adherence and smoking status, with biochemical validation of abstinence at 6 and 12 months via salivary cotinine for those not using nicotine-containing products at the time of testing. For those using nicotinecontaining products at the time of testing, carbon monoxide or anabasine (if available) will be used. See Table 2 for cut-off values. If feasible within the study timeline and staffing, health care utilization and mortality will be tracked passively over 12 months via existing databases (e.g., Tennessee Hospital Discharge Data System, TN HDDS) via exploratory Aim 3. Investigators have complementary and broad expertise to conduct MIST, the first large RCT to incorporate NMR results into clinical treatment of smoking.

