7.2 Methods and Time for Assessing, Recording, and Analyzing Safety Parameters

Participant health status will be assessed during the baseline survey to document any chronic conditions or symptoms that existed prior to the study. This list will be reviewed and compared to reported events throughout the study. If the participant reports the same symptom, occurring at the same severity, during subsequent visits, the symptom should not be recorded as an Adverse Event (AE). However, if the event is new (not previously reported) or the severity has worsened, as determined by RA, then the AE should be reported.

In the case of unresolved AEs, study staff will update the AE log if they become aware of follow-up information.

All AEs will be assessed to determine if they meet criteria for a Serious Adverse Event (SAE). If the AE is serious, then appropriate reporting measures will be followed (see section 7.5). Investigators will consult with the IRB or NIH, if uncertain how to classify an event.

7.3 Procedures for Eliciting Reports of and for Recording and Reporting Adverse Events Medical conditions/pre-existing conditions (Table 3) and medical symptoms (Table 4) will be assessed at baseline. Medical symptoms will be assessed at follow up timepoints. All events, including changes in severity of any of the below mentioned medical symptoms, will be documented in a study database.

| | Medical Condition/Pre-existing Conditions Checklist |
|----|--|
| Α | Anemia or "low blood" |
| В | Congestive Heart Failure, also called weak heart or fluid on the lungs |
| С | Dementia or "Alzheimer's" |
| D | Diabetes or high blood sugar or "sugar" |
| Е | Liver Disease or a bad liver or Cirrhosis |
| F | Chronic Hepatitis B |
| G | Chronic Hepatitis C |
| Н | High cholesterol, lipids, or triglycerides |
| Ι | Hypertension or high blood pressure |
| J | Pancreatitis |
| К | Bad nerves in your feet causing pain and numbness (neuropathy) |
| L | Bad circulation in your legs or feet |
| М | Chronic lung disease (emphysema, asthma, chronic bronchitis or chronic |
| | obstructive lung disease) |
| N | Kidney Failure (or bad kidneys) |
| 0 | Stroke or "mini" stroke (Transient Ischemic Attack) |
| P | Pneumonia |
| Q | Shingles |
| R | TB or Tuberculosis |
| S | Post-Traumatic Stress Disorder |
| Т | Schizophrenia (hearing voices or seeing things that others |
| II | Depression (depressive disorder) |
| V | Anxiety (anxiety disorder) |
| W | Bipolar Disorder |

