The informed consent document will state clearly to patients that the study is being done as a collaboration between VUMC and TelASK, a company that makes automated phone calls. Subjects will be informed that in order to make the phone calls, TelASK will be given information such as their name, study ID, phone number, sex, preference for time of call, and the date that they are discharged from the hospital or enrolled. During the study, TelASK will establish a secure website to view call results in real time, quit status, and "on-demand" counseling requests. Data will be transferred to TelASK via HIPAA-compliant secure FTP. This plan is consistent with what the VUMC IRB has approved for our ongoing NIH funded study of hospitalized smokers (5R01HL11182107: PIs [name] and [name]). Upon completion of the study, data will be transmitted back to VUMC's secure password-protected computer system. All patient data will be purged from TelASK's data files.

Data Security and Confidentiality – Samples

Blood samples used for NMR will be collected and labeled using information such as the study participant number, and/or MRN and stored in a secure location until NMR analysis is conducted by Vanderbilt Pathology Laboratory Services (VPLS), ARUP (currently contracts with VUMC) or other equivalent laboratory.

Blood or saliva for future analyses of genetics and other potentially relevant biological markers will be collected, de-identified, and stored in a secure location, in the laboratory of [name] in Light Hall. Salivary cotinine/CO samples collected for biochemical validation of self reported abstinence will be labelled with study participant number.

| Construct | Measures | Source | Baseline timepoint (CSF, | 1 | 3 | 6 | 12 |
|------------------|--|----------|--------------------------|---|---|---|----|
| | | | RASF, Baseline survey) | m | m | m | m |
| | | | | | | | |
| Sociodemographic | Age, sex, education, race/ethnicity, employment, living | Patient | Х | | | | |
| Factors | situation, health insurance type | | | | | | |
| Medical | Pre-existing condition – VACS [53]; WHI Extension | Patient/ | Х | | | | |
| Condition/Pre- | Study, HIV/AIDS [54] (Coronary heart disease, chronic | EHR/Pr | | | | | |
| existing | obstructive pulmonary disease, stroke, cancer, | оху | | | | | |
| Conditions | hypertension, diabetes, hyperlipidemia) | | | | | | |
| Checklist | Pregnancy | | Х | Х | Х | Х | Х |
| | | | | | | | |

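### The Table 4 symptom list does not prompt for rapid heartbeat, runny nose or watery eyes, which section 6.1 names as NRT effects; separately, Table 3 omits coronary heart disease, which Table 1 lists for the same checklist

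*Combined protocol and SAP*

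**What the plan says.** Section 6.1 sets out the expected effects of each product. The patch has skin irritation or itching; gum and lozenge have mouth irritation, heartburn and hiccups. For the inhaler and nasal spray, "the most common side effects can include mouth/throat irritation, coughing, runny nose, watery eyes". The next sentence reads "In rare cases dizziness, headache, nausea, and rapid heartbeat can occur". For varenicline the section names nausea and other gastrointestinal symptoms, disturbed sleep and vivid dreams.

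Section 7.3 gives the means of asking. Table 3 (conditions) and Table 4 (symptoms) are completed at baseline, and then "Medical symptoms will be assessed at follow up timepoints". Section 7.2 makes the baseline record of conditions and symptoms the comparator for later events: "This list will be reviewed and compared to reported events throughout the study". A symptom already present at the same severity is not recorded as an adverse event; a new or worse one is.

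Table 3 has one heart-disease row, "Congestive Heart Failure, also called weak heart or fluid on the lungs", alongside hypertension, lipids, leg circulation and stroke. Table 1 describes the same pre-existing conditions checklist with a list of conditions that opens "Coronary heart disease, chronic" and continues with lung disease, stroke, cancer, hypertension, diabetes and hyperlipidemia. It gives patient, EHR and proxy as sources.

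**The concern.** A symptom list used at every survey should at least cover the effects that the protocol itself tells participants and staff to expect. Rapid heartbeat is the only cardiac effect named in 6.1. The trial stratifies on cardiac admission (5.8) and makes cardiovascular instability a bar to NRT (5.3), so it is a foreseeable safety question. Runny nose and watery eyes matter for a different reason: section 2.1 notes that "some plans in Medicare Part D cover only prescription NRT (inhaler, nasal spray", so some participants on NRT may be steered to exactly those forms.

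At stake is the completeness of the adverse-event record that the DSMB monitors. An unprompted symptom tends to be reported less consistently than a prompted one. Without a prompted baseline answer, a symptom that is reported later is also harder to classify as new, worse or long-standing.

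The coronary heart disease gap is a different matter. It is an inconsistency between two descriptions of one baseline history list, and it bears on whether a later event is judged new.

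**Working it through.** The plan states no figure on this point, so the check is an item-by-item comparison.

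**Step 1. NRT effects in 6.1 against Table 4**

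| Effect named in 6.1 | Product | Table 4 row |
|---|---|---|
| Skin irritation or itching | patch | Skin irritation |
| Mouth (or throat) irritation | gum, lozenge, inhaler, spray | Mouth/throat irritation |
| Heartburn | gum, lozenge | Heartburn |
| Hiccups | gum, lozenge | Hiccups |
| Coughing | inhaler, spray | Cough |
| Runny nose | inhaler, spray | none |
| Watery eyes | inhaler, spray | none |
| Dizziness | rare | Dizziness |
| Headache | rare | Headaches |
| Nausea | rare | Nausea and/or vomiting |
| Rapid heartbeat | rare | none |

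Distinct effects: 11. Prompted: 8, and 8/11 = 73%. Not prompted: 11 − 8 = 3.

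By product group, patch, gum and lozenge have 4 of 4 prompted. The common inhaler and spray effects have 2 of 4, and the rare effects 3 of 4.

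**Step 2. Varenicline effects against Table 4.** All four named categories have at least one row: nausea, other gastrointestinal symptoms (through abdominal pain and heartburn only), sleep disturbance (insomnia) and vivid dreams (abnormal dreams).

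**Step 3. Are rows lost in the PDF?** Table 4 runs from A to Q with 17 rows; the letter M is used twice and N is absent, which accounts for all 17 places. Table 3 runs from A to Y. Neither sequence suggests a missing row, and Table 4 ends without a row for other symptoms.

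**Step 4. Other routes of capture**
- Section 7.1 defines an adverse event without reference to a list.
- Section 7.3 requires all events to be documented, with the listed symptoms as a part of them.
- Section 6.1 has participants told to report possible medication effects.
- Table 1 gives patient, EHR and proxy as sources for symptom screening.

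The three effects can therefore be recorded. None of these routes is a prompt for the symptom.

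**Step 5. Baseline comparator.** Table 4 is also the baseline symptom list. A participant who had rapid heartbeat before enrolment has no prompted baseline answer, so a later report could be taken as new under 7.2. Missing follow-up prompts tend to lower the count and a missing baseline prompt can raise it, so the net direction cannot be told from the documents.

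**Step 6. Table 1 against Table 3.** Of the seven conditions in Table 1, six have a row in Table 3: chronic lung disease, stroke, cancer, hypertension, diabetes and lipids. Coronary heart disease does not: 7 − 6 = 1 missing.

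**The case against.** The strongest reply is that recording is open. Any event is to be documented whether or not it is in Table 4, participants are told to report, and a cardiac event that leads to admission is a serious adverse event in any case. The survey instrument itself is not in the documents and may ask more than the table shows. Runny nose and watery eyes are mild local effects. Coronary history can be reached through the chart, the admission category and the discharge diagnosis. All of this stands, and it limits the point to prompting and to agreement between tables. It does not remove the point: Table 4 is the only symptom prompt described for follow-up, and Tables 1 and 3 still disagree.

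A reader might infer more than the documents support:

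- *That the list tilts safety results against varenicline.* The count of 3 unprompted NRT effects against 0 of 4 for varenicline compares single symptoms with broad categories. By rows, Table 4 prompts 8 effects named for NRT. Every participant gets the same list, both drugs are used in both arms, section 9 plans no safety comparison between drugs, and the DSMB section describes no event tables by drug.
- *That about 400 participants are never asked about rapid heartbeat.* This takes an assumed 40% NRT share of 1,000 (0.40 × 1,000 = 400), the complement of the roughly 60% varenicline prescribing in the pilot. The rare-effects sentence follows the inhaler and spray sentence and may apply only to those forms, whose share is not given; the number concerned could be anywhere from none to all of the 400. Being unprompted is also not the same as a missed harm.
- *That the missing coronary row hides NRT harms.* Coronary heart disease is not an effect named in 6.1, and Table 3 is a history list. Its absence would more likely make an old problem look new.

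**Conclusion.** The point holds as a minor and cheaply corrected gap. Three of the 11 NRT effects named in section 6.1, including the only cardiac one, have no prompt in Table 4 at baseline or follow-up. They rely on unprompted capture and have no prompted baseline comparator. Separately, one of the seven conditions that Table 1 gives for the pre-existing conditions checklist is absent from Table 3, and the two must be reconciled.

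The conclusion assumes that the surveys in use follow Tables 3 and 4 as printed. If the REDCap forms already carry these items, only the protocol tables need correcting. No event rate is given, so the number of events missed cannot be estimated. The primary analysis and power are unaffected, and no bias between arms or between drugs is shown.

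**What to change.** 1. Add rapid or pounding heartbeat, runny nose, watery eyes and an open row for other symptoms to Table 4, at baseline and at all four follow-ups. Correct the repeated letter M at the same time.
2. Add coronary heart disease to Table 3 so that it matches Table 1. Back-fill it from the EHR, which Table 1 already names as a source, for those already enrolled.
3. Record the date of the change. When the new symptoms are summarised, state how many participants were asked at each survey and separate those with a baseline answer from those without.

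The cost is four symptom rows, one condition row, a REDCap edit and a chart look-up for those already enrolled. The drawback is that surveys already completed lack the new symptom items, so counts before and after the change are not directly comparable. No treatment or eligibility rule changes.
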